6.4 PROTOCOL DEVIATIONS

Subjects with such non-compliance will be determined prior to database lock. Major protocol deviations will be summarized in the CSR. This summary will include the number and percent of subjects (overall and by site) with each deviation type.

Major deviations in this study include, but not limited to the following:

- Inadequate or delinquent informed consent
- Inclusion/exclusion criteria not met
- Unreported serious adverse events or fall event

SAP: COP-0001
Active Protective Technologies, Inc

- Materially inadequate record keeping
- Intentional deviation from protocol, Good Clinical Practice, or regulations by study personnel

6.5 MULTIPLE COMPARISONS AND MULTIPLICITY

There is one primary effectiveness endpoint, and it will be compared between treatment groups at a one-sided 0.025 level of significance, adjusting for propensity score (PS). There are three secondary endpoints that will also be tested using propensity score adjusted test of proportions, and the type I error rate will be adjusted for multiple testing.

To control type I error, the three secondary endpoints will be tested in a hierarchical, gatekeeping manner in the order specified below, each at a one-sided 0.025 level of significance, and only after the primary study effectiveness endpoint has been achieved in favor of the test treatment. Further, each secondary endpoint numbered 2 through 3 below will be tested for significance between treatments only if the previous secondary endpoint in the list has been shown to be significantly beneficial for the test treatment.

This hierarchical closed test procedure is used to account for multiple testing with the goal of controlling the "maximum overall Type I error rate", which is the maximum probability that has been prespecified that one or more null hypotheses are rejected incorrectly, at a one-sided 0.025 level of significance.

- 1. The proportion of Hip fractures due to fall in the subjects receiving SOC as compared to subjects receiving SOC plus the Tango Belt.
- 2. The proportion of ED visits due to fall in the subjects receiving SOC as compared to subjects receiving SOC plus the Tango Belt.
- 3. The proportion of Hospitalizations due to fall in the subjects receiving SOC as compared to subjects receiving SOC plus the Tango Belt.

There will be no adjustment for multiple comparisons across any remaining effectiveness endpoints, nor will there be adjustment for multiple comparisons across ancillary endpoints.

6.6 DEMOGRAPHICS

Subject demographics and baseline characteristics for the Safety, ITT, and HC populations will be summarized in a table. Sex, race, ethnicity, and mobility level will be summarized with frequency and percent.

Age will be summarized with number of observations, mean, median, minimum, maximum, and standard deviation.

7 EFFECTIVENESS ANALYSES

Given that subjects in the two comparison groups (Tango Belt vs. SOC) are not randomized and thus may not have balanced baseline characteristics, Propensity Score (PS) matching will be carried out to adjust for measured baseline confounders prior to any statistical test(s) comparing treatments on effectiveness endpoints at the interim and final analysis.

7.1 Propensity Score Method

For each subject, a PS (i.e., predicted probability between 0 and 1) of intervention group membership (Tango Belt vs. SOC) will be calculated using a logistic regression, with "intervention group" as the outcome and the following baseline variables as the predictors: Age, mobility level, sex, and whether the subject fell in the past year.

Once propensity scores are calculated, propensity score matching (PSM) without replacement will be performed.

Subjects in the intervention group (i.e., Tango Belt) will be matched to controls with a similar PS using nearest neighbor matching (NNM) at a ratio of 1:2.

The PS modeling and design will be performed by a statistician who will be blinded to the endpoint data for each subject to avoid introducing bias into the analysis. The blinded endpoint data includes the primary and three secondary endpoints listed in section 3.2.

Balance of baseline variables (e.g., continuous variable, dichotomous variable, interaction terms, or squares of continuous variable) will be assessed by comparing the pre-matched and post-matched datasets.

Adequacy of propensity balance will be assessed by examination of standard differences between groups to confirm standard difference in post-matched dataset does not exceed 10%. Additionally, a comparison of the baseline covariate variables between groups after adjusting for propensity subgroup will be carried out as in D'Agostino et al. If the propensity matching is adequate, this will result in non-significant p-values (p>0.05) for the baseline characteristics.

Additional PS methods may be employed if group balance is not achieved by NNM, examples include covariate adjustment, inverse probability of treatment weighted (IPTW), etc.

Since enrollment may be ongoing at the time of interim analysis, propensity score modeling and matching will be conducted at the interim analysis and subjects will be rematched at the time of the final analysis to ensure the best PS match possible. With PS matching possibly occurring twice the following differences in PS modeling and design may occur:

- 1. Subjects may be matched to different control subjects.
- 2. The number of matches (1:1 or higher to a maximum of 1:4) may change based upon enrollment ratios.

3. The technique used to match (i.e., NNM) may change to another PS method to ensure adequacy of propensity balance.

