- 2. Have experienced a fall-related fracture after age 50
 - Have experienced one or more falls in the 12-months prior to consent and have a diagnosis of osteoporosis, osteopenia, or prescribed osteoporosis medication.
- 3. Independently or with staff or caregiver assistance, able to transfer between surfaces (e.g., to or from a bed, chair, wheelchair, toilet, standing position) or walk or move between locations (use of an assistive device such as a walker is acceptable);
- 4. Have a waist circumference between 29 50 inches (63.5 127 cm);
- 5. Able to comply with required study procedures and follow-up schedule as determined by the Study Investigator;
- 6. Are under the care of the Investigational organization;
- 7. Provides consent or their legally authorized representative provides consent on subject's behalf

Exclusion Criteria (ANY of the following criteria):

- 1. Age 64 years or less;
- 2. Participation in a different clinical investigation that can conflict with this clinical study as determined by the Study Investigator and approved by the Sponsor;
- 3. Total dependence on staff or caregiver assistance to be able to transfer between surfaces (e.g. to or from a bed, chair, wheelchair, toilet, standing position) and walk and move between locations:
- 4. Use of other devices or interventions outside of SOC for fall risk management during study participation without Sponsor approval;
- 5. Unable to comply with required study procedures and follow-up schedule as determined by the Study Investigator;
- 6. Does not provide consent, or legally authorized representative does not provide consent

Investigational Device Tango® Belt

Route of Administration The Tango Belt is a device intended to be worn around the waist and is designed to:

- Recognize serious hip-impacting falls in progress
- Deploy an airbag upon detection of a serious hip-impacting fall in progress to protect the hip region from potential major injury
- Communicate fall and impact alerts to designated persons

Schedule of Visits The study is composed of the following study intervals:

Baseline Enrollment, screening, and provision of Tango Belt

14-day Run-in for adherence screening90-days EMR screening for endpoints

180-days EMR screening for endpoints and completion of participation

Table of Contents

Title Page 1					
List of Abbreviations and Definition of Terms 2					
Protocol Summary/Protocol Synopsis 3					
1.	Key Roles				
	1.1	Key roles listed	8		

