4.4 Endpoints

Primary Endpoint: The primary outcome measure will be the proportion of major hip injuries due to fall in the subjects receiving SOC as compared to subjects receiving SOC plus the Tango Belt.

Secondary Endpoints: Secondary outcome measures include the proportion of each of the following:

- Hip fractures due to fall in the subjects receiving SOC as compared to subjects receiving SOC plus the Tango Belt.
- Emergency Department visits due to fall in the subjects receiving SOC as compared to subjects receiving SOC plus the Tango Belt.
- Hospitalizations due to fall in the subjects receiving SOC as compared to subjects receiving SOC plus the Tango Belt.

Ancillary Endpoints: Ancillary endpoints will include:

- Adverse events
- Major injuries due to fall
- Fall occurrence
- Device wear adherence
- Device fall alerts
- Device discrimination of serious hip-impacting vs. non-serious hip and non-hip impacting falls
- Airbag deployment
- FES-I short version

5. Selection of Subjects

- **5.1 Inclusion Criteria**: All subjects are required to meet ALL of the following inclusion criteria to be considered eligible for participation in this study:
 - 1. Age 65 years or older;

- 2. Have experienced a fall-related fracture after age 50 -OR-
 - Have experienced one or more falls in the 12-months prior to consent and have a diagnosis of osteoporosis, osteopenia, or prescribed osteoporosis medication.
- Independently or with staff or caregiver assistance, able to transfer between surfaces (e.g., to or from a bed, chair, wheelchair, toilet, standing position) or walk or move between locations (use of an assistive device such as a walker is acceptable);
- 4. Have a waist circumference between 29 50 inches (63.5 127 cm);
- 5. Able to comply with required study procedures and follow-up schedule as determined by the Study Investigator;
- 6. Are under the care of the Investigational organization;
- 7. Provides consent or their legally authorized representative provides consent on subject's behalf
- **5.2 Exclusion Criteria**: Subjects will be excluded from participating in this study if they meet ANY of the following exclusion criteria:
 - 1. Age 64 years or less;
 - 2. Participation in a different clinical investigation that can conflict with this clinical study as determined by the Study Investigator and approved by the Sponsor;

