7.3 Study Visit Descriptions

Visit 1 Baseline:

• Informed Consent will include the provision of the Informed Consent Form (ICF) with overview of the clinical study proposed and informational materials that may include: video description, flyer and discussion of the Tango Belt technology. Informed consent will be obtained in person by qualified clinical study site personnel delegated to this task by the site investigator and before any study related procedures and/or assessments can be performed. If the subject has a legally authorized representative (LAR) documented as a person of authority (POA), that person identified in the EMR will be contacted with the same information and presented with the ICF. If there is telephonic agreement of study consent, this will be noted by the CRA on the ICF with date, time and indication of LAR, with tow (2)

copies sent via email or USPS to the LAR for final signature. An email including the ICF with explanation of the clinical study and inclusion of the noted information can also be shared with a LAR for electronic signature for subject informed consent. Contact information for the clinical site study investigator will be provided to the subject/LAR to offer communication in regard to any questions or concerns for consenting to participation in the clinical study. The subject will be provided the Short version of the FES-I if they have the cognitive capability to do so. BIMS score of 13-15 indicates ability to take the Short version of the FES-I.

- The subject will be assigned a Tango Belt of the correct size based on measuring their waist size and the belt will be introduced to the subject with specific fitting applied using the sizing strap for best comfort. The Tango Belt assignment will be performed using the Tango Belt Companion App to allow for data tracking for this subject. An order for wearing of the Tango Belt will be applied to the medical chart and the care team will be notified of the patient's inclusion in the study with attention for wear adherence and charging cycle.
- The baseline metrics of medical and fall history, fall mitigation plan, and mobility level will be taken directly from the MDS and/or EMR within the electronic documentation system utilized at the clinical study site.

Visit 2 Run-in period (14 days +/- 2):

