5 ANALYSIS POPULATIONS

5.1 HISTORICAL CONTROL POPULATION

The Historical Control Population (HC) for this study includes retrospective subjects that meet all inclusion and exclusion criteria except for the waist circumference and need for consent. Eligible subjects' electronic health records will be mined for the baseline, midpoint, and final study metrics.

The investigator or a designee will retrospectively review the site's electronic medical record (EMR) database to determine long-term care patient population's eligibility for meeting the study inclusion criteria. The subjects in the clinical site census at the time frame 6 months prior to the IRB approval date will be screened for eligibility for study inclusion.

If there is an insufficient number of eligible subjects to meet the control group target (defined as 2 times the expected number of intervention group subjects to be enrolled from the site) at 6 months prior to the intervention group start date, the EMR database screen will extend retrospectively in 6 month increments until the control group target is reached.

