7.2 PRIMARY EFFECTIVENESS ANALYSIS

The primary effectiveness endpoint for this study is the proportion of subjects experiencing major hip injuries due to falls, as reported at the 180-day visit and will be presented for the Tango Belt and control groups using the ITT and adherence populations.

The proportion of subjects experiencing major hip injury due to falls is defined as the total number of subjects who experience a major hip injury due to a fall divided by the total number of subjects.

The primary effectiveness hypotheses are:

$$\begin{array}{l} H_0 \colon \pi_T \ \geq \ \pi_C \\ H_1 \colon \pi_T \ < \pi_C \end{array}$$

where π_T and π_C are the proportion of subjects experiencing major hip injuries due to falls in the Tango Belt and control group, respectively.

The null hypothesis (H_0) for this endpoint states that the true proportion of subjects using Tango Belt and experiencing major hip injuries due to falls is greater than or equal to the true proportion of subjects in the control group who experience major hip injuries due to falls. The alternative hypothesis (H_1) states that the true proportion of subjects using Tango Belt and experiencing major hip injuries due to falls is less than the true proportion of subjects in the control group who experience major hip injuries due to falls.

The proportion of major hip injuries by treatment group will be presented along with a 95% confidence interval using the Clopper-Pearson method. H_0 will be tested at a one-sided 0.025 level of significance using a logistic regression analysis to compare treatment groups while controlling for propensity score.

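### The propensity score carries fall history only as yes/no for the past year, so a group difference in fall frequency, if there is one, is largely left out of the matching and the adjusted test

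*Combined protocol and SAP*

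**What the plan says.** - **Propensity model (SAP 7.1).** The predictors of group membership are "Age, mobility level, sex, and whether the subject fell in the past year". No fall count is listed.
- **Eligibility (protocol 5.1, criterion 2).** A subject qualifies by "Have experienced a fall-related fracture after age 50" or by the second route, "Have experienced one or more falls in the 12-months prior to consent and have a diagnosis of osteoporosis, osteopenia, or prescribed osteoporosis medication". Controls meet the same criteria except waist circumference and consent (protocol 5.3, SAP 5.1).
- **Use of the score.** Matching is "nearest neighbor matching (NNM) at a ratio of 1:2", without replacement (SAP 7.1). The primary test is made "using a logistic regression analysis to compare treatment groups while controlling for propensity score" (SAP 7.2), and the secondary endpoints use the same model (SAP 7.3). No other covariate enters.
- **Balance (SAP 7.1, 6.6).** The limit is a 10% standardized difference on baseline variables. Fall count is not named, and the demographic table has no fall-history item.
- **Data.** At Visit 1, "The baseline metrics of medical and fall history, fall mitigation plan, and mobility level will be taken directly from the MDS and/or EMR" (protocol 7.3). For controls, "Eligible subjects' electronic health records will be mined for the baseline, midpoint, and final study metrics" (SAP 5.1).

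**The concern.** The comparison is not randomized, and SAP section 7 relies on the propensity score to deal with baseline confounding. The endpoint is injury from a fall, so how often a resident falls is close to a direct measure of exposure to it. For fall-route entrants the one fall-history term is constant. For fracture-route entrants it separates no falls from some, but not one from several. At equal scores, a belt subject with one prior fall and a control with five are treated as exchangeable.

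A difference in frequency could arise because belt subjects must consent and then wear the device in a 14-day run-in, while controls come from past census records with neither step. If belt subjects fall less often, an ineffective belt looks protective. If they fall more often, a real benefit is partly hidden.

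**Working it through.** **1. The plan's own figure.** The documents give no figure for this point, so the check starts from the sample size that sets the precision. Pocock spending at half information gives 0.025 × ln(1 + (e − 1) × 0.5) = 0.0155 one-sided. With 15% against 3% (80% reduction), 80% power, 1:2 allocation and a continuity correction, n = 94 belt subjects, as in SAP section 4. This takes 15% as the proportion over follow-up. The final size is 188 against 376 (SAP section 2).

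**2. Risk by fall count (assumed).** Let prior-year falls be gamma-Poisson with mean m and shape k, and let injury risk be proportional to a resident's underlying fall rate. The expected rate given n falls is proportional to k + n, so risk relative to one fall is (k + n)/(k + 1), averaged over n for the 3+ group. Among residents with at least one fall:

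| m, k | Share 1 / 2 / 3+ | Relative risk 1 / 2 / 3+ | Mean relative risk |
|---|---|---|---|
| 1.5, 1 | 0.40 / 0.24 / 0.36 | 1 / 1.50 / 2.75 | 1.75 |
| 2, 1 | 0.33 / 0.22 / 0.44 | 1 / 1.50 / 3.00 | 2.00 |
| 2, 2 | 0.33 / 0.25 / 0.42 | 1 / 1.33 / 2.13 | 1.56 |

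**3. Bias with an inert belt (assumed imbalance).** Move 10 points of the belt group from 3+ falls to one fall. The apparent risk ratio is 1 − 0.10 × (RR₃₊ − 1)/mean:

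- (1.5, 1): 1 − 0.10 × 1.75/1.75 = 0.900
- (2, 1): 1 − 0.10 × 2.00/2.00 = 0.900
- (2, 2): 1 − 0.10 × 1.133/1.556 = 0.927

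The opposite shift gives 1.07 to 1.10. The 10-point shift is a standardized difference of about 0.21 on the 3+ indicator, for example 0.10/√[(0.36 × 0.64 + 0.26 × 0.74)/2] = 0.22. That is about twice the SAP's own limit.

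**4. Type I error at 188/376, 15% control risk.** Use Φ[(Δ − 1.96 × SE₀)/SE₁], with SE₀ pooled and SE₁ unpooled, treated as a single test at one-sided 0.025. For a ratio of 0.900, p_T = 0.135, Δ = 0.015, SE₀ = 0.0315 and SE₁ = 0.0310, giving 6.6%. For 0.927 the result is 5.1%.

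**5. Milder settings.** If only 70% of subjects carry the difference and the rest have the same mean risk, the ratios are 1 − 0.7 × 0.10 = 0.93 and 1 − 0.7 × 0.073 = 0.95, with type I error of about 5% and 4%. A 5-point shift halves the bias, to 0.95 to 0.96 with everyone affected.

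**6. Simulation of SAP 7.1 and 7.2, null belt effect, 188/376, 2,000 runs per setting.** Assumed: 70% fall route; Poisson falls, with one certain fall added for fall-route entrants; 0.35 log-odds of injury per fall; control risk about 15%; age, sex and mobility unrelated to falls.

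| Mean Poisson falls, belt / control | Fall term in score | Median odds ratio | Type I error | Standardized difference of count after matching |
|---|---|---|---|---|
| 1.5 / 1.5 | yes/no | 1.00 | 2.1% | 0.00 |
| 1.0 / 1.5 | yes/no | 0.84 | 9.1% | −0.42 |
| 1.0 / 1.5 | count added | 0.99 | 2.5% | −0.42 |
| 0.75 / 1.5 | yes/no | 0.78 | 13.4% | −0.65 |
| 0.75 / 1.5 | count added | 0.99 | 2.2% | −0.65 |

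The imbalances here are larger than in steps 3 to 5. The last column matters for the fix. With a pool of two controls per belt subject and 1:2 matching without replacement, nearly every control is used, so matching does not balance the count. The correction comes through the score in the regression. With 94 belt subjects and a pool of 376, adding the count brought the difference to −0.04 or better. The simulated count was a linear term capped at six, not the four categories proposed below.

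**The case against.** The strongest reply is that the harm is conditional. Nothing in the documents shows that the groups differ in fall frequency, and with equal frequency the yes/no model is unbiased. Every input to the size beyond 188/376 and 15% is an assumption, and moving the whole shift from 3+ falls to exactly one fall is towards the high end. All of that stands, and is why the result is given as a range.

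Four stronger readings are tempting but not supported:

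- **That staff choose who is offered the belt by fall history.** Protocol 5.3 offers participation to those who pass record screening and the waist measurement. Only the ability-to-comply criterion leaves discretion.
- **That fall frequency goes wholly unadjusted.** Whatever part age, sex and mobility explain is adjusted.
- **That the balance checks cannot reveal the problem.** SAP 7.1 speaks of baseline variables generally and does not exclude a count. It simply does not name one, so nothing requires the check.
- **That this could produce the design effect.** Apparent reductions of 5% to 10% in steps 3 to 5 are far below the 60% and 80% targets.

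Other omitted covariates, such as BIMS score or site, may also matter, and fall count is not shown to outrank them. It is, however, closely tied to the endpoint. There are also practical objections: controls with missing data are dropped (SAP 6.2.2), a count needs fuller records than a yes/no, and the casebook that would show whether a count was captured is not among the documents. These bear on how to make the change, not on whether the gap exists.

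**Conclusion.** The point holds in conditional form. The plan has no term for fall frequency beyond a yes/no that is fixed for fall-route entrants, and no later step is required to supply one. If the belt group has a 10-point lower share of residents with three or more falls, an inert belt shows a risk ratio of 0.90 to 0.93 and type I error of about 5% to 6.6% when all subjects are prior-year fallers. With 70% affected, these become 0.93 to 0.95 and about 4% to 5%. The reverse imbalance costs power.

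These figures rest on assumed gamma-Poisson falls with mean 1.5 to 2, risk proportional to fall rate, and an imbalance that the documents neither show nor rule out. The change should be made because it is cheap and the score is the main protection against confounding, not because bias has been demonstrated.

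**What to change.** In SAP 7.1, replace the yes/no term with the number of falls in the 12 months before the index date, in categories 0, 1, 2, and 3 or more, from the MDS/EMR in both groups. Define the index date as consent for belt subjects and the start of the 6-month observation window for controls. This is needed because the eligibility window, "Have experienced one or more falls in the 12-months prior to consent", refers to an event that controls do not have. These falls precede belt use, so belt alerts cannot affect the count.

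Report the count's standardized difference before and after matching. Because the control target in SAP 5.1 equals the 1:2 ratio, expect that matching alone may not balance it. Keep the revised score in the outcome regression and, if the 10% limit is exceeded, add the count as a covariate. Covariate adjustment is already a listed fallback in 7.1.

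The cost is two extra model terms, a count field in the chart extraction if only yes/no was captured, and possible loss of controls whose count is missing. That loss can be limited by keeping the yes/no value with a missing-count category, which needs a stated exception to SAP 6.2.2.

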4.1 INTERIM ANALYSES

The study will incorporate a group sequential design (GSD) in which an interim analysis will be performed to detect an 80% protective effect of the Tango Belt at 80% power. If a significant difference is found between the prospective Tango Belt subjects and historical controls at the interim analysis, the study will be stopped, and the Tango Belt deemed superior to SOC alone. If not, sample size reestimation will be completed, and enrollment will continue until a final sample size is reached to detect a 60% protective effect of the Tango Belt at 80% power and a 5% total level of significance.

Following the steps from section 4, we assumed subjects were followed for an average of 6 months, an annual fall-with-major-hip-injury rate of 15%, and sufficient historical control subjects to allow 1:2 allocation of subjects to treatment and control. This would require 134 subjects in the prospective Tango Belt group and 268 subjects in the historical control group at the interim analysis using the Pocock alpha-spending function as well as accounting for 30% attrition. At the end of the study (should the higher effectiveness target not be achieved at interim analysis), 268 total subjects would be required in the prospective Tango Belt group and 536 subjects would be in the historical control group.

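### At the planned two-to-one control pool, SAP 7.1's 1:2 matching without a stated caliper selects every control and leaves balance unchanged; separately, the propensity score omits fracture history and bone status

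*Combined protocol and SAP*

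**What the plan says.** SAP 7 makes propensity-score matching the step that deals with measured baseline confounding before groups are compared, at the interim and at the final analysis. SAP 7.1 estimates the score from four variables, "Age, mobility level, sex, and whether the subject fell in the past year". It then matches without replacement: belt subjects "will be matched to controls with a similar PS using nearest neighbor matching (NNM) at a ratio of 1:2". No caliper is given.

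The planned pool has the same ratio. SAP 2 and 4 give 94/188 and 188/376 before attrition and 134/268 at the interim after it. For the end of the study, SAP 4.1 says "268 total subjects would be required in the prospective Tango Belt group and 536 subjects would be in the historical control group". SAP 5.1 extends control screening backwards in six-month blocks until the site has twice its expected belt enrolment.

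Balance is to be confirmed by a "standard difference in post-matched dataset does not exceed 10" per cent. In addition, "a comparison of the baseline covariate variables between groups after adjusting for propensity subgroup will be carried out", with p>0.05 expected for each variable. If balance is not reached, "Additional PS methods may be employed if group balance is not achieved by NNM, examples include covariate adjustment" and weighting. At the final rematch, "The number of matches (1:1 or higher to a maximum of 1:4) may change based upon enrollment ratios", and the technique may also change for the sake of balance.

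The primary and secondary tests (SAP 7.2 and 7.3) are logistic regressions that control for the propensity score. Inclusion criterion 2 (Protocol 5.1) admits a subject by either of two routes: a fracture from a fall after the age of 50, or a fall in the past year together with a diagnosis of osteoporosis or osteopenia or the use of osteoporosis medication.

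**The concern.** Matching improves balance by leaving out unsuitable controls. If two distinct controls per belt subject are taken from a pool that holds exactly two per belt subject, none is left out. The step that SAP 7 relies on then adjusts nothing, and balance is whatever the pool happened to have. The 10% limit is likely to fail, and the SAP does not require a particular response. The analysis behind the primary result would then be settled only after the covariate data have been seen.

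The second gap is independent of the first. Of the facts that make a subject eligible, the score carries only the past-year fall. Prior fracture and bone status bear directly on the chance of a major hip injury. A propensity term cannot adjust for variables that are not in the score, and the imputation model in SAP 6.3.1 does not contain them either.

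**Working it through.** **Planned sizes.** Reading 15% as the six-month control proportion, one-sided 0.025, Pocock-type spending at half the information (interim alpha 0.025 × ln(1 + (e − 1) × 0.5) = 0.0155; final nominal alpha 0.0139) and a continuity-corrected test at 1:2:
- interim, 15% v 3%: 94 belt subjects (SAP: 94)
- final, 15% v 6%: 185 (SAP: 188, within 2%)
- attrition: 94/0.70 = 134.3, 188/0.70 = 268.6, 376/0.70 = 537.1 (SAP: 134, 268, 536)

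**Matching at that pool.** Controls needed are 2 × 134 = 268 and 2 × 268 = 536; controls available are 268 and 536. All are used. In simulation (covariates assumed independent, mobility at four levels) every control was selected in every dataset. With an assumed age gap of 0.3 SD, the standardised difference was 0.30 before and after matching.

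**Away from exactly 2:1** (same assumed gap, 1:2 matching):

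| Belt : control | Caliper | Age difference before → after |
|---|---|---|
| 268 : 590 | none | 0.29 → 0.17 |
| 214 : 536 | none | 0.30 → 0.10 |
| 134 : 536 | none | 0.29 → 0.03 |
| 134 : 268 | 0.2 SD of logit | 0.30 → 0.12 (91% of belt subjects matched) |
| 268 : 536 | 0.2 SD of logit | 0.30 → 0.13 (94% matched) |
| 134 : 188 | none | 0.30 → 0.77 (70% matched, highest score first) |

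SAP 6.2.2 drops controls with missing information. If a share L is lost from 536, the belt subjects without two controls number 268 − 536(1 − L)/2 = 268L. That is about 13, 27 and 80 at L = 5%, 10% and 30%.

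**Chance failure of the 10% limit.** With no true difference, a standardised difference has standard error √(1/n_T + 1/n_C).
- 134/268: √(3/268) = 0.1058; P(|d| > 0.10) = 0.345; any of four = 1 − 0.655⁴ = 0.82
- 268/536: √(3/536) = 0.0748; P(|d| > 0.10) = 0.181; any of four = 1 − 0.819⁴ = 0.55

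Checking mobility level by level (seven terms) raises these to 93% and 74% in simulation. The p-value check is far looser. Even unadjusted, d = 0.10 corresponds to p = 0.34 and 0.18, and p = 0.05 is reached only at d = 0.207 and 0.147. Adjusted for propensity subgroup, it passed in at least 99% of simulated trials with no true difference and in 92% to 98% with the 0.3 SD gap. With that gap the 10% limit failed in about 99% or more.

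**Does the primary test suffer from the matching?** With the propensity term and no omitted factor, the simulated null odds ratio was 0.99 to 1.01 and one-sided rejection 2.5% to 2.6%.

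**Omitted fracture status.** Null simulation at 268/536, 3,000 datasets per cell, event proportion 7.5% or 15%. Assumed: 70% past-year fallers, non-fallers all qualifying by fracture, and half of control fallers with a fracture.

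| Factor OR / prevalence gap among fallers | Belt less fragile: OR, error | Belt more fragile: OR, error |
|---|---|---|
| 1.5 / 10 points | 0.97–0.98, 2.9–3.1% | 1.03, 1.6–2.1% |
| 2 / 15 points | 0.93, 4.0–4.5% | 1.06–1.07, 0.9–1.4% |
| 3 / 25 points | 0.84, 7.2–11.2% | 1.16–1.17, 0.3–0.7% |

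The Monte Carlo standard error is √(0.025 × 0.975/3000) = 0.29 points, so the mildest case is barely distinguishable from 2.5%. A separate run of the less-fragile case gave 3.4%, 4.5% and 10.0% without the factor. With it in the score and the planned regression unchanged, these became 2.9%, 2.0% and 2.7%.

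**The case against.** The sizes are planning figures. Screening in six-month blocks can overshoot, run-in failures shrink the belt group, and the table shows that a modest surplus lets matching work. This stands: the result is exact only at 2:1, and the realised ratio is not in the documents.

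SAP 4.1.1 plans for belt subjects who find no adequate match, which implies an adequacy rule. This also stands in part. Such a rule would let matching do something, but SAP 7.1 does not define one. At 1:2 the illustrative caliper still leaves 0.12 to 0.13, above the limit.

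A reader might infer that the primary comparison is unadjusted or biased because matching is inert. The documents do not support that: SAP 7.2 and 7.3 control for the score in every test, and the simulated size is nominal for the scored covariates. Nor do they support replacing that regression. At 188/376 with a 60% effect, a 15% six-month control proportion and the assumed age gap, power before any Pocock adjustment was 88% as planned, 86% with weighting to the belt group and 76% with 1:1 caliper matching.

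A reader might infer that the two balance checks contradict each other. They can both be required; they differ in stringency. A reader might also suspect an outcome-driven choice of method. SAP 7.1 blinds the propensity statistician to the endpoints and ties a change of technique to balance. What remains is that the change is permitted rather than required, that the fallbacks have no order, and that the change of ratio follows enrolment rather than balance.

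**Conclusion.** The point holds as two gaps in pre-specification that should be fixed. First, at the planned pool of exactly two controls per belt subject, the matching in SAP 7.1 cannot change balance. The 10% limit would then fail by chance in about 82% (134/268) and 55% (268/536) of trials, assuming four independent covariates, with no determined next step. Surplus controls or an adequacy rule would soften this; control losses would leave some belt subjects short. No bias in the primary test is shown from this alone.

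Second, prior fracture and bone status are outside the score and unadjusted throughout. It is tempting to read this as inflated type I error, but the documents give neither the size nor the direction of any imbalance. About 3% to 11% applies only under the assumed gaps with belt subjects less fragile; with belt subjects more fragile the test is conservative (0.3% to 2.1%).

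**What to change.** Before any outcome analysis:

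1. Add to the score a fracture from a fall after the age of 50 (yes/no) and bone diagnosis or medication (yes/no). Where only the qualifying route was recorded, use the route, so that controls are not lost under SAP 6.2.2. Keep the propensity-adjusted logistic regression as the primary test.
2. For a pool near 2:1, state that the primary analysis uses all eligible controls with that regression, or that matching uses a stated caliper. If matching is kept, 1:1 balances better than 1:2: at the assumed gap, 1:1 from the same pool left 0.02 to 0.03.
3. State that the 10% limit on the scored covariates governs and that the subgroup p-values are descriptive. Say on which data the limit is measured. If all controls are kept, the raw difference is the one that fails by chance, so measure it after stratifying by the score. Name one fallback. Overlap weighting is a candidate, though it shifts the estimand to the overlap population and makes the scored differences zero by construction.
4. Define the matching rate in SAP 4.1.1 by the same adequacy rule, and bring SAP 5.2 to 5.2.3 into line.

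Cost: SAP wording and modest programming, with some chart re-abstraction if the bone items were not recorded (the case report forms are not in the documents). An illustrative 0.2 SD caliper drops 6% to 9% of belt subjects at 1:2. At 1:1 it drops 2% to 3% and leaves about half the controls unused, with the loss of power shown above. Keeping all controls avoids that loss.
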